10.4.5 Incidence of Hypoglycemic Events

CGM will be conducted throughout the study from Dose 1 through EOS visit for safety monitoring and insulin use adjustments. The CGM data collected during this period will be analyzed separately for Parts A and B for the incidence of hypoglycemic events.

A hypoglycemic event is defined as an incident where the glucose value obtained from the CGM in a previous timepoint is higher than 70 mg/dL, but drops to 70 mg/dL or less in the subsequent timepoint with the low CGM glucose reading lasting at least 10 minutes. Each event will be counted even when multiple events occur on the same day, however if consecutive readings of GCM are deemed low then only a single event will be counted. The frequency of hypoglycemic events will be summarized by treatment group and timepoint (week). The categories for this frequency summary are as follows:

- Subjects with no hypoglycemic events
- Subjects with 1 to 5 hypoglycemic events
- Subjects with 6 to 10 hypoglycemic events
- Subjects with 11 to 15 hypoglycemic events
- Subjects with 16 or more hypoglycemic events

The same summary will be repeated for the second hypoglycemic threshold, where a hypoglycemic event is defined as an incident where the glucose value obtained from the CGM in

a previous timepoint is 54 mg/dL or higher, but drops below 54 mg/dL in the subsequent timepoint.

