Subjects must be seated or in a semi-recumbent position for at least 5 minutes prior to vital signs measurement. All measurements will be recorded in the source documents and recorded on the appropriate eCRF page. Any abnormal measurements may be repeated and reported on the eCRF page with appropriate source documentation. When vital signs and blood sample collection occur at the same time, vital signs should be performed before blood samples are drawn.

Electrocardiogram

Twelve-lead ECGs reporting ventricular rate, PR, QRS, QT and QTcF intervals will be obtained by the Principal Investigator or designee at the time points indicated in the

Schedule of Assessments ([Appendix A](#)). Subjects should be supine for at least 5 minutes before each ECG is obtained. A single ECG will be performed at screening.

At the Baseline Visit, ECGs will be performed (in triplicate approximately one minute apart) will be considered baseline ECGs. All other ECG collections will be single tracings. When ECG and blood sample collection occur at the same time, ECGs should be performed before blood samples are drawn.

The Principal Investigator or qualified designee will review all ECGs. The original ECG tracings will be maintained in the source documentation of each subject.

Adverse Events and Concomitant Medications

Subjects will be assessed for adverse events ([Section 9](#)) and concomitant medications (including non-prescription medications and/or supplements such as protein / amino acid supplements) at least daily during residency periods and during each outpatient visit as outlined in the Schedule of Assessments ([Appendix A](#)). Any rescue medications and use of meals/food to manage hypoglycemic sensations or events will be reviewed carefully with the subject and recorded accordingly. Any AEs or concomitant medication use reported throughout the study will be recorded in the eCRF with appropriate source documentation.

Continuous Glucose Monitoring (CGM) and Glucose Blood Monitoring

Subject's glucose levels will be monitored using the DexCom CGM device. The CGM device will be used to track blood sugar levels day and night, and it will collect readings automatically every 5 minutes. CGM uses a tiny sensor placed under the skin of the subject's belly and measure blood glucose levels.

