12 CHANGES FROM THE PROTOCOL SPECIFIED STATISTICAL ANALYSES

The product of the ratio of average glucose obtained from the CGM at Day 78 (Week 12) and Baseline; and the ratio of average insulin use obtained from the insulin diary at Day 78 (Week 12) and Baseline, were not statistically analyzed with repeated measures ANCOVA since this is not a metric assessed at multiple timepoints. The definition of a hypoglycemic event was updated after the 1st interim of Part A to be defined as an incident where the glucose value obtained from the CGM in a previous timepoint is higher than 70 mg/dL, but drops to 70 mg/dL or less in the subsequent timepoint with the low CGM glucose reading lasting at least 10 minutes.

Additional analysis of the LDL cholesterol data has been added.

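### The CGM hypoglycemia count has no recovery rule, so one 5-minute reading above 70 mg/dL can split a shallow episode into several events

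*SAP*

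**What the plan says.** SAP 10.4.5 opens an event when "the glucose value obtained from the CGM in a previous timepoint is higher than 70 mg/dL" and the next value "drops to 70 mg/dL or less in the subsequent timepoint with the low CGM glucose reading lasting at least 10 minutes". Repeats count in full: "Each event will be counted even when multiple events occur on the same day". The only text that bears on when an event finishes is the merging clause, "if consecutive readings of GCM are deemed low then only a single event will be counted". Neither document states an end-of-event rule or a minimum time above 70 mg/dL before another event may begin. On sampling, the CGM subsection of Protocol section 7 says that "it will collect readings automatically every 5 minutes".

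The second threshold is defined by a change in which "a previous timepoint is 54 mg/dL or higher, but drops below 54 mg/dL in the subsequent timepoint". No duration is attached to it. For both thresholds the output is the number of subjects per week and treatment group in five bands: 0, 1–5, 6–10, 11–15, and 16 or more events.

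SAP section 12 records that "The definition of a hypoglycemic event was updated after the 1st interim of Part A" and gives the 10-minute wording as the updated form. Incidence of hypoglycemic events is a secondary endpoint in Protocol section 10.

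**The concern.** At 70 mg/dL the rule is asymmetric. An event needs 10 minutes of low readings to start, but one 5-minute reading above the line both breaks the run and supplies the higher prior value that a new event requires. A trace sitting just under 70 mg/dL crosses the line through sensor noise alone. A trace well below it does not.

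The number of events per episode therefore depends on how close the episode lies to the threshold. If treatment changes the depth or length of lows, the arms could show different event counts for the same number of episodes. Hypoglycemia is a main safety question for a drug meant to reduce insulin need, so its count should not depend on an unstated end rule.

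**Working it through.** The documents give no event rate for this endpoint, so there is no figure to reproduce. The rule was coded as written and applied to 5-minute readings.

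**Inputs from the documents:** thresholds (≤ 70 and < 54 mg/dL), the 10-minute start condition at 70, merging of consecutive lows only (SAP 10.4.5), and the 5-minute interval (Protocol section 7).

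**Assumptions:** 10 minutes means two low readings or three (10 minutes elapsed), both tried. The comparison rule ends an event only after three consecutive readings above threshold (15 minutes). Noise and glucose distributions are as stated below.

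**1. Constructed traces at 70 mg/dL, events counted**

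| Trace | SAP rule, 2-reading start | SAP rule, 3-reading start | 15-min recovery (2 / 3) |
|---|---|---|---|
| 75, 69, 69, 71, 69, 68, 72, 69, 69, 80 | 3 | 0 | 1 / 0 |
| Three lows then one 71, four times (60 min low) | 4 | 4 | 1 / 1 |
| Alternating 69 and 71 (30 min low) | 0 | 0 | 0 / 0 |
| Unbroken, nadir 40 (70 min low) | 1 | 1 | 1 / 1 |

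The first trace has three low runs of two readings each, so the choice between two and three readings moves it from 3 events to 0. The second trace splits under either reading. In the third, no low run lasts long enough to count.

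**2. Simulated single episodes** (flat plateau, noise SD 1.5–4 mg/dL, lag-1 correlation 0.5), mean events per episode

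| Episode | SAP rule, 2-reading start | With 15-min recovery | SAP rule, 3-reading start |
|---|---|---|---|
| 60 min, nadir 69 | about 1.6 | about 1.1 | 1.1–1.3 |
| 60 min, nadir 67 | 1.1–1.7 | 1.0–1.1 | 1.0–1.3 |
| 60 min, nadir 60 | 1.00–1.05 | 1.00 | about 1.0 |
| 90 min, nadir 69 | 2.0–2.4 | 1.1–1.4 | 1.6–1.8 |

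**3. Simulated weeks** (100 subjects, 2016 readings each, mean 160, SD 60 mg/dL, independent noise). Excess = mean count under the SAP rule ÷ mean count with 15-minute recovery − 1.

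| Noise SD | 2-reading start | 3-reading start |
|---|---|---|
| 0 | 8.47/8.19 − 1 = 3% | 8.13/7.94 − 1 = 2% |
| 2 | 8.87/8.30 − 1 = 7% | 8.12/7.82 − 1 = 4% |
| 3 | 9.39/8.48 − 1 = 11% | 8.45/7.97 − 1 = 6% |
| 5 | 10.10/8.24 − 1 = 23% | 8.43/7.49 − 1 = 13% |

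Further simulated weeks gave about 3–17%. With noise SD 1.5–4 and mean 150–160, 81–95% of subject-weeks stayed in the same reporting band.

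**4. The 54 mg/dL threshold.** With no start duration, a trace alternating 53 and 55 (six low readings) gives 6 events at < 54 and 1 event under the 70 mg/dL rule. Simulated 60-minute episodes at nadir 53 count 2.2–2.4 times, against 1.2–1.4 with 15-minute recovery and the same one-reading start.

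**5. What the end rule cannot change.** With the start condition held fixed, a recovery rule only merges events. A subject has at least one event under both rules or under neither. The zero-event band is unaffected, except for an episode that straddles a week boundary.

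**The case against.** The strongest reply is that little depends on this count. The table is descriptive, with wide bands and no test or confidence interval, and most subject-weeks keep their band. SAP 10.3.4.4 also compares percent time below 70 mg/dL between arms with 95% confidence intervals and p-values, and that measure does not depend on how lows are split. The < 54 mg/dL summary speaks to depth. All of this stands and limits the weight of the point. It does not correct the count itself. The time-below-range analysis covers only selected weeks, whereas the event count is planned from Dose 1 onward.

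The large multiples come from artificial plateaus 1–3 mg/dL below the line, and the noise values have no source in the documents. That also stands, which is why the weekly excess is the better guide to size. Fifteen minutes is likewise a choice the documents do not supply.

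A reader might infer that the rule could reverse the safety comparison between arms. Nothing here shows that. No two-arm comparison was simulated, and a similar excess in every arm would leave their ordering unchanged. A reversal would need a large treatment effect on episode depth, which would have to be assumed.

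A reader might also take the 54 mg/dL definition to have the same asymmetry. It does not: one reading opens the event and one closes it. Nor does section 12 say why the definition was changed after the interim, so the documents do not support reading the change as driven by results.

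**Conclusion.** The point holds as a counting defect of modest size. SAP 10.4.5, followed exactly, can count one shallow episode more than once. A deep episode counts once because it is unbroken, not because of its depth as such. Multiple counting requires brief re-crossings with each low run long enough to qualify; shorter runs count as nothing.

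The total excess is roughly 3–17% in simulated weeks. It is lower with a three-reading start and reaches 23% only at a noise SD of 5 mg/dL with a two-reading start. These sizes rest on assumed noise and glucose distributions. The excess could differ between arms if treatment shifts episode depth or length, but neither document gives data to say that it does. At 54 mg/dL the fault is a missing duration as well as a missing recovery rule, and flicker counts more there.

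**What to change.** In SAP 10.4.5, before database lock:

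- State that an event ends only when readings stay above 70 mg/dL (at or above 54 mg/dL for the second threshold) for at least 15 minutes, that is, three consecutive readings. Lows before that belong to the same event.
- State whether 10 minutes of low glucose means two readings or three.
- Apply the same start duration at 54 mg/dL.
- Report counts under the present definition alongside, because the definition has already been changed once after an interim, and record the change in SAP section 12.

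The cost is a short text change, a few lines of code and one repeated table per threshold. The downside is that true episodes less than 15 minutes apart are merged.

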Appendix A. Schedule of Assessments – Part B

Study Period (or Dose #)	Screen	Lead-In	Dose 1		Dose 2	Dose 3	Dose 4	Dose 5	Dose 6	Dose 7	Dose 8
Study Week	≤ 42 days		1		2	3	4	5	6	7	8
Study Day		1 to 2 Weeks	Baseline/ Pre-dose	1	8 ± 1	15 ± 1	22 ± 1	29 ± 1	36 ± 1	43 ± 1	50 ± 1
Informed consent	X										
Medical History ^a	X		X								
Physical examination	X		X					X			
Height (Screening only) & Body weight	X	X	X					X			
Urine pregnancy test (women); FSH ^f	X		X					X			
Urine drug/alcohol test	X		X					X			
12-lead ECG ^b	X		X					X			
Vitals (BP, RR, HR, T) ^c	X	X	X		X	X	X	X	X	X	X
Chemistry, Hematology, Lipid Panel, and Urinalysis ^e	X		X		X	X		X		X	
Fasting (≥ 8-hr) plasma glucose ^e			X		X	X	X	X	X	X	X
Serum Ketones & Free Fatty Acids ^e			X		X	X	X	X	X	X	X
Study Drug SC Administration				X	X	X	X	X	X	X	X
Seven-point blood glucose profile ^d		X					X				X
Blinded Continuous Glucose Monitoring (CGM) ^g		X		X			X				X
Daily insulin usage dairy ^h		X	X	X	X	X					X
HbA1c	X		X						X		
Insulin, C-peptide, GLP-1, and Glucagon ^e			X					X			
Serum PK sample collection ^e			X		X			X			
Anti-REMD-477 Ab sample collection ^e			X								
Exploratory biomarker collection ^e			X								
Liver Injury Biomarkers ^e			X					X			
Liver MRI/ FibroScan ^j			X								
QOL Questionnaires ⁱ			X								
Con-Med monitoring	X		◀	▶							
Adverse event monitoring			◀	▶							

Footnote Key:

- a. Medical history includes significant past medical events (e.g. prior hospitalizations or surgeries), a review of diabetes history and glycemic control, and any concurrent medical illnesses.
- b. After the Screening Visit, 12-lead ECG to be performed in triplicate, approximately 1 min apart. When ECG and blood sample collection occur at the same time, ECGs should be performed before blood samples are drawn.
- c. Vital signs include blood pressure, respiratory rate, heart rate, and oral temperature.
- d. Seven-point blood glucose profile will measure glucose by finger stick over three consecutive days before and 2 hours after each meal, and at bedtime.
- e. Sample should be collected pre-dose on all dosing days.
- f. FSH required at screening for post-menopausal women.
- g. Blinded CGM will be performed for one week during the Lead-in Period (completed prior to the Baseline Visit), and for one week after Doses 1, 4, 8 and 12. CGM data will be downloaded at the clinical research unit during scheduled site visits, as indicated in the Schedule of Assessments.

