5.2 Secondary Objectives

- To compare the effects of multiple doses of REMD-477 versus placebo on measures of glycemic control including change from baseline at Week 13 in fasting glucose and glucose area under the curve (AUC) after mixed meal tolerance test (MMTT) – Part A only.
- To compare the effects of multiple doses of REMD-477 versus placebo on change from baseline at Week 12 in average daily 24-h blood glucose concentration and time within target range as assessed by continuous glucose monitoring (CGM) and seven-point glucose profile.

- To compare the effects of multiple doses of REMD-477 versus placebo on the product of the ratio of average glucose (Week 12/Baseline) and ratio of average insulin use (Week 12/Baseline).
- To evaluate the safety and tolerability of multiple doses of REMD-477 versus placebo.
- To compare the incidence of hypoglycemic episodes after multiple doses of REMD-477 versus placebo.
- To compare the effects of multiple doses of REMD-477 versus placebo on change from baseline at Week 13 in hemoglobin A1c (HbA1c).
- To compare the proportion of subjects who achieve HbA1c reduction of $\geq 0.4\%$ after multiple doses of REMD-477 versus placebo at Week 13.
- To compare the effects of multiple doses of REMD-477 versus placebo on pancreatic beta cell function as measured by change from baseline at Week 13 in C-peptide AUC after a MMTT and arginine challenge test (for a subset of subjects who were enrolled prior to Protocol Amendment #1) – Part A only.
- To compare the effects of multiple doses of REMD-477 versus placebo on pancreatic alpha cell function as measured by change from baseline at Week 13 in peripheral levels of fasting glucagon, active and total glucagon-like peptide 1 (GLP-1), and glucagon and GLP-1 (active and total) AUC after MMTT – Part A only.
- To determine REMD-477 plasma concentrations and formation of anti-REMD-477 antibodies after multiple dosing.

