10 STATISTICAL METHODOLOGY

10.1 General

Data listings will be provided for the All Subjects Population. Summary statistics and statistical analyses will be performed for subjects included in the relevant analysis populations (Safety/PK/PD).

For continuous data, summary statistics will include the arithmetic mean, arithmetic standard deviation, median, minimum, maximum, and number. For log-normal data (eg, the Mixed Meal Tolerance Test [MMTT] parameters: areas under the concentration-time curve [AUCs]), the geometric mean and geometric coefficient of variation (CV%) will also be presented. For categorical data, frequency counts and percentages will be presented. Data listings will be provided for all subjects. For the calculation of summary statistics and statistical analysis, unrounded data will be used.

Outputs will be created separately for Parts A and B.

Missing values will not be imputed.

Data analysis will be performed using SAS® Version 9.4.

Analysis Data Model (ADaM) datasets will be prepared using Clinical Data Interchange Standards Consortium (CDISC) ADaM Version 2.1, and CDISC ADaM Implementation Guide Version 1.1. Pinnacle 21 Community Validator Version 2.2.0 will be utilized to ensure compliance with CDISC standards.

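### Hypoglycemic event incidence has a comparative objective, but the SAP gives it only a binned weekly table with no rate per observed CGM time and no between-arm estimate

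*SAP*

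**What the plan says.** **Objective.** SAP 5.2, like the protocol's objectives, includes: "To compare the incidence of hypoglycemic episodes after multiple doses of REMD-477 versus placebo". Incidence of hypoglycemic events is also listed among the protocol's secondary endpoints.

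**Planned output.** SAP 10.4.5 defines an event by a downward crossing of 70 mg/dL on CGM and repeats the summary for crossings below 54 mg/dL. The analysis is this: "The frequency of hypoglycemic events will be summarized by treatment group and timepoint (week"). The categories are none, 1 to 5, 6 to 10, 11 to 15, and 16 or more; the second reads "Subjects with 1 to 5 hypoglycemic events". Parts are kept apart: "The CGM data collected during this period will be analyzed separately for Parts A and B for the incidence of hypoglycemic events".

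**General rules.** SAP 10.1 adds "For categorical data, frequency counts and percentages will be presented" and "Missing values will not be imputed". Neither rule sets a minimum wear time or a time denominator.

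**Collection period.** SAP 10.4.5 opens with "CGM will be conducted throughout the study from Dose 1 through EOS visit". The Part B schedule in Appendix A (footnote g) gives, after the lead-in week, "for one week after Doses 1, 4, 8 and 12". Protocol Section 7 ends CGM collection at the Day 85 visit for Part A subjects ongoing or newly enrolled at Amendment 2.

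**Related analysis.** SAP 10.3.4.4 takes percent CGM time below 70 mg/dL over 7 days. It analyses the change from baseline by repeated measures ANCOVA in each Part, with difference from placebo, 95% CI and p-value. The CGM weeks analysed there are those after Doses 4, 8 and 12, plus Weeks 16 and 20.

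**The concern.** The objective asks for a comparison, and the event analysis stops at a table. Other parts of the SAP's safety section (LDL cholesterol, pulse and blood pressure, QT and QTcF) specify a difference from placebo with a CI and p-value, although none of them has a comparative objective of its own. SAP Section 12 revises the event definition but does not explain why no contrast is planned.

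Two things are at stake. Less hypoglycemia is part of the protocol's rationale for reducing insulin, so a reader will want an effect size for events, and a five-bin table by week does not yield one. In addition, the number of events counted in a week depends on how long the sensor was recording. Without a time denominator, a shift toward the low bins may reflect benefit or lost data.

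**Working it through.** **1. The plan's own figures.** The documents give no sample size, event rate or precision for CGM-defined hypoglycemia. Their only power figure concerns insulin use. It is 2 × (1.96 + 0.84)² × (0.36/0.30)² = 22.6, so 23 per group against the stated 22 or more. The input used below is the planned 25 per arm per Part. Event rates and dispersion are assumptions throughout. The protocol's background figure of two symptomatic episodes per week is not a CGM event rate.

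**2. Can the table separate fewer events from less wear?** Expected weekly count = true rate × fraction of the week recorded.
- Assume 4 events per week and full wear. A 30% reduction gives 4 × 0.70 = 2.8. No reduction with 70% wear also gives 4 × 0.70 = 2.8. The expected tables are the same.
- With a negative binomial of dispersion 1, P(0) = 1/(1 + mean) and P(6 or more) = (mean/(1 + mean))⁶.

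| Expected count | 0 events | 1–5 | 6 or more |
|---|---|---|---|
| 4.0 | 20.0% | 53.8% | 26.2% |
| 2.8 (either cause) | 26.3% | 57.7% | 16.0% |

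- With a Poisson count at 2 per week, the split over 0, 1–5 and 6 or more is 13.5% / 84.8% / 1.7%. Halving the rate or halving wear gives 36.8% / 63.2% / 0.1% in both cases.
- If wear were 70% in one arm and 90% in the other at equal true rates, the apparent rate ratio would be 0.70/0.90 = 0.78, a 22% apparent reduction. That imbalance is an illustration.

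**3. What would a rate model deliver?** Take 4 versus 2.8 events per week, 25 per arm and between-subject variance v. Over T weeks the half-width on the log rate ratio is 1.96 × √[2v/25 + (1/(4T) + 1/(2.8T))/25].

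| v | 12 weeks (Part A): half-width; factor | 4 weeks (Part B): half-width; factor |
|---|---|---|
| 0.25 | 0.29; ×/÷ 1.34 | 0.32; ×/÷ 1.37 |
| 0.5 | 0.40; ×/÷ 1.49 | 0.42; ×/÷ 1.52 |
| 1 | 0.56; ×/÷ 1.75 | 0.58; ×/÷ 1.78 |

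Varying the rate from 2 to 10 per week with the same rate in both arms and v = 0.5 to 1 gives ×/÷ 1.48–1.76 over 12 weeks and 1.49–1.80 over 4 weeks. At an observed ratio of 0.70 over 12 weeks, the upper limits are 0.94, 1.05 and 1.23 for v = 0.25, 0.5 and 1; two of the three exceed 1. This ignores any gain from a lead-in covariate.

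**4. Collection period.** Set side by side, SAP 10.4.5 describes continuous CGM to end of study and applies it to both Parts. The Part B schedule yields four post-dose weeks (1, 4, 8 and 12). Part A subjects ongoing or enrolled at Amendment 2 have none after Day 85. The sentence holds only for earlier Part A subjects.

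**The case against.** The strongest reply is that hypoglycemia is already formally compared: percent time below 70 mg/dL in SAP 10.3.4.4 is scaled to time and tested against placebo in each Part. A reader of 10.4.5 alone might infer that the plan cannot compare hypoglycemia at all, and that would be wrong. The reply narrows the gap without closing it. Duration is not episode count, there is no 54 mg/dL version although the protocol names that as its second threshold, and the analysed weeks omit Week 1, when dosing starts.

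Other points stand in the plan's favour.
- The event table is by arm, week and Part, so it allows a descriptive comparison over nominally equal 7-day windows. A reader might infer that the spread in collection from about 4 to 24 weeks biases it. It does not, because the two Parts are never pooled and each cell covers one week.
- A reader might infer that subjects without sensor data are counted as having no events. Nothing in the SAP says so, and the rule against imputation points the other way, though it is not an explicit rule for this table. Denominators may be set in the table shells, which are not available here. Partial wear within a week remains.
- The bins do register an effect: the share with 6 or more events falls from 26% to 16% in the example above.
- No passage suggests that wear differs between the blinded arms.
- The protocol assigns no test to hypoglycemia and plans descriptive statistics for safety data, so protocol and SAP agree. With 25 per arm a model will often be inconclusive. That argues for estimation rather than a formal test; it does not argue against a rate and an interval.

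**Conclusion.** The point holds in limited form. Event incidence, a secondary objective worded as a comparison, receives only a descriptive binned table with no rate per observed CGM time, no between-arm estimate and no CI. In that table partial wear cannot be told apart from fewer events; at any assumed rate, 70% wear reproduces a 30% reduction exactly. The formal comparison of time below 70 mg/dL is a partial substitute. The collection-period sentence in SAP 10.4.5 contradicts the schedules and needs correcting whatever is decided about the model.

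This is an inexpensive improvement to a secondary safety analysis and does not affect the primary result. The structural findings rest on the text. The numerical illustrations rest on assumed event rates, dispersion and wear, because the documents supply none of these for CGM-defined events.

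**What to change.** In SAP 10.4.5:

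1. For each threshold (70 and 54 mg/dL) and each Part, add a negative binomial model of treatment-period events, with treatment, lead-in CGM event rate as covariate and log(observed CGM time) as offset. Report each dose-placebo rate ratio with its 95% CI, labelled as estimation. Lead-in CGM is scheduled in both Parts.
2. Show CGM person-days by arm in the weekly tables, and base the weekly percentages on subjects with CGM data in that week.
3. Correct the collection-period sentence: Weeks 1, 4, 8 and 12 for Part B; through Day 85 for Part A subjects ongoing or enrolled at Amendment 2; through end of study for earlier Part A subjects.

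The cost is SAP wording and one extra model on data already collected. The downside is modest precision, about ×/÷ 1.3 to 1.8 under the assumptions above, so a 30% reduction may be inconclusive and the text should say so in advance.

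### SAP 10.4.5 sets a 10-minute duration rule for the ≤70 mg/dL event but none for the <54 mg/dL event, so the two hypoglycemia tables are neither comparable nor nested

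*SAP*

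**What the plan says.** SAP section 10.4.5 defines hypoglycemic events from CGM at two thresholds.

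- **First threshold.** Glucose is above 70 mg/dL, then "drops to 70 mg/dL or less in the subsequent timepoint with the low CGM glucose reading lasting at least 10 minutes".
- **Counting.** Several events on one day all count, but if consecutive readings are low, "then only a single event will be counted".
- **Second threshold.** "The same summary will be repeated for the second hypoglycemic threshold, where a hypoglycemic event is defined as an incident" in which the earlier value "is 54 mg/dL or higher, but drops below 54 mg/dL in the subsequent" reading. The definition ends there and gives no duration.
- **Output.** For each threshold, subjects are tabulated by treatment group and week in bands of 0, 1 to 5, 6 to 10, 11 to 15, and 16 or more events.

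SAP section 12 records that "The definition of a hypoglycemic event was updated after the 1st interim of Part A". It then gives only the 70 mg/dL wording with the 10-minute rule and does not mention 54 mg/dL.

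Protocol section 7 (Day 1 treatment) sets ≤70 mg/dL as the primary threshold and <54 mg/dL as the second, with no duration for either. The CGM subsection says of the device that "it will collect readings automatically every 5 minutes". Incidence of hypoglycemic events is a secondary endpoint in protocol section 10.

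**The concern.** Every reading below 54 is also at or below 70, so a reader will take the second table as a subset of the first. As written it is not. The first rule discards excursions shorter than 10 minutes, while the second counts every downward crossing, including a single 5-minute reading. A trace that hovers around 54 inside one long low episode therefore adds one event to the first table and several to the second.

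The practical risk is twofold. Comparing the two tables within an arm would mix a difference in glucose threshold with a difference in counting rule. And because the text calls the second table a repeat of the first but gives it its own definition, two programmers could in good faith produce different <54 tables from the same data.

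**Working it through.** **1. The two rules side by side**

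| Element | ≤70 mg/dL event | <54 mg/dL event |
|---|---|---|
| Previous reading | >70 | ≥54 |
| Next reading | ≤70 | <54 |
| Minimum duration | 10 minutes | none stated |
| Sampling (protocol section 7) | every 5 minutes | every 5 minutes |

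One isolated reading falls short of 10 minutes, so it fails the first rule and meets the second.

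**2. Both rules applied literally to short traces** (illustrative values, not trial data). Results are the same whether 10 minutes is read as two or as three consecutive readings.

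| 5-minute trace (mg/dL) | As written: ≤70, <54 | 10-minute rule at both: ≤70, <54 |
|---|---|---|
| 95, 88, 52, 82, 96 | 0, 1 | 0, 0 |
| 95, 78, 66, 60, 52, 61, 68, 77, 90 | 1, 1 | 1, 0 |
| 90, 76, 66, 58, 53, 55, 53, 56, 52, 57, 66, 75, 88 | 1, 3 | 1, 0 |
| 95, 74, 64, 53, 51, 50, 58, 66, 76 | 1, 1 | 1, 1 |

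Row 1 is the isolated reading that counts only at the lower threshold. Row 3 is one ≤70 episode counted three times at <54.

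**3. Possible size under assumptions.** The documents give no CGM mean, SD, autocorrelation, noise or event rate, so every input here is assumed. The model is a first-order autoregressive 5-minute trace with mean 150, SD 50, lag-1 correlation 0.985 and added noise SD of 0, 2 or 4 mg/dL. It was simulated for 4,000 subject-weeks of 7 × 24 × 12 = 2,016 readings. A sustained event is a crossing followed by at least one further reading below 54, that is, 10 minutes read as two readings.

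Check of the normal case without noise: z = (54 − 150)/50 = −1.92. Expected crossings per week = 2,016 × [Φ(z) − Φ₂(z, z; 0.985)] ≈ 8.8. The simulation gives 8.7.

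| Marginal | Noise SD | <54 events per week, as written | With 10-minute rule | Ratio |
|---|---|---|---|---|
| Normal | 0 | 8.69 | 5.49 | 1.6 |
| Normal | 2 | 9.16 | 5.63 | 1.6 |
| Normal | 4 | 10.37 | 5.91 | 1.8 |
| Lognormal | 0 | 0.65 | 0.38 | 1.7 |
| Lognormal | 2 | 0.83 | 0.41 | 2.0 |
| Lognormal | 4 | 1.55 | 0.57 | 2.7 |

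The weekly rates differ more than tenfold between the marginals at zero noise, so they say nothing about this trial. The ratio is steadier. Reading 10 minutes as three readings would disqualify more dips, so the ratios would be larger.

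**4. Which mechanism dominates.** In the same runs, under 1% of <54 crossings were isolated readings with both neighbours above 70 (row 1). Almost all of the excess comes from brief dips inside longer ≤70 episodes (rows 2 and 3).

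**The case against.** **Carry-over may be intended.** The second table is introduced as a repeat of the first, and the single-event counting rule is not restated for 54 mg/dL either, though it presumably applies. Section 12 also speaks of the event definition in general terms. This is a plausible reading and may be what was meant. But the SAP gives an explicit second definition that omits the clause, and section 12 does not supply it. The ambiguity stands.

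**A looser rule at 54 may be deliberate.** Counting every <54 crossing is a defensible, more sensitive safety count. The protocol sets no duration at either threshold and does not say that they must share one. But the SAP neither states this choice nor gives a reason for it.

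**The output is modest.** It is a banded descriptive table with no test, interval or model. CGM time below 70 mg/dL is analyzed separately (SAP 10.3.4.4) and does not use this event rule. This stands and limits the importance of the point.

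**Stronger readings that the documents do not support.**

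- A reader might infer that the main harm is a brief reading counted at <54 but not at ≤70. That needs the whole ≤70 excursion to last under 10 minutes, which was rare in every assumed trace.
- A reader might infer that sensor artefacts inflate the <54 count. The documents give no artefact rate, and in the model short dips are common even with zero noise.
- A reader might infer that a treatment difference would be blurred. The same rule applies in every arm, and no such effect has been shown.
- The omission looks like an incomplete revision after the Part A interim, but the documents do not say so.

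**Conclusion.** The inconsistency is in the current SAP text and does not depend on any simulation: a 10-minute rule at ≤70 mg/dL, none at <54 mg/dL, and no explanation. With 5-minute readings, the two tables are neither comparable nor nested, and one ≤70 episode can produce several <54 events.

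Its size in this trial cannot be derived from the documents. Under the assumed traces, with 10 minutes read as two readings, <54 counts as written are about 1.6 to 1.8 times (normal marginal) or 1.7 to 2.7 times (lognormal marginal) those under the duration rule. These ranges are illustrative only.

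The point concerns a descriptive summary of a secondary safety endpoint. It leaves the primary endpoint, sample size and power untouched. It should be corrected, but it does not threaten the trial's main conclusion.

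**What to change.** In SAP 10.4.5, before database lock:

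1. Add to the <54 mg/dL analysis definition the clause already used for 70 mg/dL, "with the low CGM glucose reading lasting at least 10 minutes".
2. State how many consecutive 5-minute readings make 10 minutes, and that the consecutive-reading rule applies at both thresholds.
3. List single-reading <54 values separately by subject, so that no safety information is lost.
4. Record the change in section 12. If the sponsor prefers to count every <54 crossing, say so there with the reason, and footnote the table as using a different rule.

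With items 1 and 2, each <54 event lies within a ≤70 excursion that also meets the duration rule. The <54 count could still exceed the ≤70 count when one ≤70 episode contains two sustained dips below 54, and a table footnote should say so.

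The cost is one clause, one line of code and one listing. The small downside is that brief <54 dips leave the main count, which the listing offsets. The change concerns how events are counted for analysis, not clinical management.
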